**Role of Enhancing Serotonin Receptors Activity for Sleep Apnea Treatment in
Patients With SCI**

NCT02458469

[name], PhD

3/12/2020

Study Protocol: A pilot randomized placebo-controlled cross-over study. Eligible subjects with spinal cord injury were studied on three separate occasions: (1) Buspirone vs. Trazodone vs. placebo for 2 weeks; the participants were blinded to what medication they were taking. The initial dose of Buspirone is 15 mg daily (7.5 mg b.i.d.). Buspirone dosage was increased 5 mg per day at intervals of 2 to 3 days until a maximum dose of 30mg/day is reached. Trazodone was given at 100 mg dose before bed-time. After the two week treatment, a noninvasive nasal mechanical ventilation study was repeated to determine the hypocapnic apneic threshold. (2) Cross over medication for two weeks was followed by a second noninvasive nasal mechanical ventilation study to determine the hypocapnic apneic threshold followed by two weeks washout. (3) Cross over medication for two weeks was followed by another study to determine the hypocapnic apneic threshold. For the baseline hypocapnic apneic threshold the nasal mechanical ventilation study obtained from specific aim 1 was used as a baseline.

Statistical Data analysis: The primary endpoint is the CO₂ reserve ($\Delta P_{ET}CO_2-AT$) which is a marker to measure susceptibility to hypocapnic central apnea, defined as the difference between average end-tidal CO₂ ($P_{ET}CO_2$) for the control breaths on room air and the breaths before the cessation of noninvasive nasal mechanical ventilation. The standard statistical package SPSS (Sigmstat, version 3.5) was used for data analysis. A detailed descriptive analysis of all quantitative data was performed involving the summarization of data, and normal distribution. The primary analysis was repeated measure analysis of variance. In the absence of normal distribution of data, appropriate non-parametric tests were used.

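### A two-week washout is stated between periods 2 and 3 but none between periods 1 and 2, so the period-2 study can fall 2 weeks after the previous drug against at least 4 for period 3: a minor, cheaply fixed carryover risk

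*Combined protocol and SAP*

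**What the plan says.** All the relevant text is in the combined protocol and SAP, under Study Protocol and Statistical Data analysis.

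- The design is described as "A pilot randomized placebo-controlled cross-over study", with buspirone, trazodone and placebo each taken for two weeks.
- Step (1) ends with the measurement: "After the two week treatment, a noninvasive nasal mechanical ventilation study was repeated to determine the hypocapnic apneic threshold". No washout is stated after it.
- Step (2) opens with the next treatment: "Cross over medication for two weeks was followed by a second noninvasive nasal mechanical ventilation study". It closes with the only washout in the document, two weeks long: "second noninvasive nasal mechanical ventilation study to determine the hypocapnic apneic threshold followed by two weeks washout".
- Step (3) follows that washout: "Cross over medication for two weeks was followed by another study to determine the hypocapnic apneic threshold".
- On analysis: "The primary analysis was repeated measure analysis of variance". No period, sequence or carryover term is mentioned.

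The document gives no treatment orders, no sample size, no reason for the washout length, and no interval between the step (1) study and the start of step (2). The only baseline described is one ventilation study taken from specific aim 1, so no separate baseline is described for each period.

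**The concern.** The move from period 1 to period 2 and the move from period 2 to period 3 are the same kind of transition, from one study treatment to the next. The protocol thought a two-week washout worthwhile at one of them and states none at the other, without giving a reason.

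If any drug or withdrawal effect from period 1 lasted into the period-2 study, it would be mixed into the CO₂ reserve recorded for the period-2 treatment. The primary comparison is made within participants across periods, so such an effect would enter the drug-placebo contrasts directly. With no baseline for each period, there is no measurement that would reveal a residual effect. What is at stake is how cleanly the period-2 results can be read.

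**Working it through.** The plan states no figure on this point, so there is nothing to reproduce. Treatment and washout lengths come from steps (1) to (3). Lambda, treatment orders, sample size and half-lives are assumptions, because the document gives none of them.

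**1. Gap from the last dose of the previous drug to the next study** = washout + 2 weeks on the new treatment.

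| | Period 2 | Period 3 | Minimum schedule |
|---|---|---|---|
| As written | 0 + 2 = 2 weeks | 2 + 2 = 4 weeks | 2 + 2 + 2 + 2 = 8 weeks |
| Washout at both transitions | 2 + 2 = 4 weeks | 2 + 2 = 4 weeks | 2 + 2 + 2 + 2 + 2 = 10 weeks |

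The gaps are minimums, since any unstated interval would lengthen them.

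**2. Effect of carryover into period 2 only.** Let A and B be the two drugs, P placebo, and e_A and e_B the drug effects against placebo. Lambda is the share of the previous drug's effect that is still present at the period-2 study.

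*Six orders used equally.* In period 2, A follows B once and P once, B follows A once and P once, and P follows A once and B once. The shifts in the treatment means are:
- A: lambda × e_B/6
- B: lambda × e_A/6
- P: lambda × (e_A + e_B)/6

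The shift in A − P is therefore −lambda × e_A/6. By symmetry, B − P shifts by −lambda × e_B/6. Each drug's contrast is diluted by lambda/6 of its own effect, and the other drug's carryover cancels.

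| Lambda (assumed) | 0 | 10% | 25% | 50% |
|---|---|---|---|---|
| Dilution, lambda/6 | 0 | 1.7% | 4.2% | 8.3% |

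*One Latin square (A-B-P, B-P-A, P-A-B).* In period 2, B follows A, P follows B and A follows P. Then:
- A − P shifts by −lambda × e_B/3
- B − P shifts by lambda × (e_A − e_B)/3

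A single drug's carryover thus moves a contrast by 0 to lambda/3 of the *carrying* drug's effect, and the contrast moved may be the other drug's. With both drugs carrying over and effects equal and opposite, B − P moves by 2 × lambda/3. If every participant took A-P-B, A − P would move by lambda itself. So lambda/3 is not a ceiling.

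Under the six-order and single-Latin-square layouts, adding period terms leaves the carryover shifts unchanged.

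**3. How much drug could remain** (assumed half-lives, share = 2^(−t/half-life)). At 2 weeks (336 hours):
- 24 h: 0.006%
- 48 h: 0.8%
- 72 h: 3.9%
- 120 h: 14%

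At 4 weeks, the 120 h figure falls to 2.1%.

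**4. Cost of period terms** (assumed 6 participants × 3 periods). Residual df without them are 18 − 1 − 5 − 2 = 10, and with them 10 − 2 = 8. With balanced orders the drug-placebo variance stays at 2σ²/6 = 0.333σ². The 95% half-width goes from 2.228 × √0.333 = 1.286σ to 2.306 × √0.333 = 1.331σ, a ratio of 1.035. With 12 participants (22 to 20 df) the ratio is 2.086/2.074 = 1.006.

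**5. What period terms protect against.** Suppose a linear drift of d per period and no period term. The bias in a drug-placebo contrast is 0 with six equal orders. It is up to 2d/7 = 0.29d if one of the six orders is used twice (7 participants), and up to 2d/5 = 0.40d if one is missing (5 participants).

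**The case against.** The strongest reply is that the design already supplies a washout before the period-2 study. Each study comes after two weeks on the new regimen, so at least two weeks off the period-1 drug have passed, which is the length the protocol itself chose as a washout. Under the assumed half-lives, less than 1% of the drug remains at that point for any half-life up to 48 hours. This stands, and it is why the risk is rated small. It does not exclude a longer-lasting pharmacodynamic or withdrawal effect, on which the document is silent.

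A second reply is that this may be a drafting omission. The protocol is a short summary, mostly in the past tense ("Eligible subjects with spinal cord injury were studied on three separate occasions"), and a washout after period 1 may have been used and left out. The document cannot settle this, so a reader who infers that the washout was definitely omitted goes further than the text allows.

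A third reply is that the sizes rest wholly on assumed carryover, orders and numbers. That also stands. They show how a given carryover would feed through, and they are not evidence that any occurred.

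Finally, period terms address drift and not carryover, so they are a companion improvement and not a cure for the missing washout. That is correct, and the fix says so.

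**Conclusion.** The asymmetry is real on the text, and nothing elsewhere in the document repairs it. The minimum gap before the study is 2 weeks in period 2 and 4 weeks in period 3. It is a minor point, and correcting it is a cheap improvement to interpretability.

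A reader might infer that the period-2 results, or the trial's conclusions, are biased by carryover. The documents do not support that. They report no residual effect, two weeks off drug precede the period-2 study in any case, and if nothing persists to that study there is no bias. A reader might also take 16.7% (lambda/3 at lambda = 50%) as an upper limit on the distortion. It is not one: it applies to one drug's carryover taken alone in a single Latin square, and it is a share of the carrying drug's effect. Nor does the text support either 50% carryover or a single Latin square.

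The most interpretable illustration is the dilution of lambda/6 with six equal orders: 1.7% at lambda = 10% and 8.3% at 50%. The lower end is more plausible given the built-in gap. This rests on assumed carryover, assumed orders, and carryover at the 1-to-2 transition only.

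**What to change.** - **Clarify.** State whether a washout followed period 1 and how long it was. This takes a sentence.
- **Any participant still to cross over, or a follow-on trial.** Apply the same two-week washout at both transitions, so that both later studies fall at least 4 weeks after the previous drug. The cost is two more weeks per participant (minimum 8 to 10).
- **Data already collected.** Fit the repeated-measures ANOVA with participant, period and treatment effects. This costs 2 residual df: an interval about 3.5% wider with an assumed 6 participants, or 0.6% with 12. It protects against period drift when orders are unequal and does not remove carryover.
- **If there was no washout after period 1.** Report the treatment orders, the number of participants in each, and the shorter gap before period 2 as a limitation. This takes a few sentences.

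A previous-treatment term for period 2 is at most an optional post hoc sensitivity analysis. With 6 assumed participants it leaves 6 df and raises the contrast variance from 0.333σ² to 0.381σ² (six orders) or 0.667σ² (one Latin square). Compared with the period model, the interval is 13% or 50% wider (1.510/1.331 or 1.998/1.331), which is too costly for the main analysis of a pilot.

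### The primary analysis names a repeated-measures ANOVA but no drug-versus-placebo contrast, so the stated test does not say whether buspirone or trazodone differs from placebo

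*Combined protocol and SAP*

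**What the plan says.** The Study Protocol paragraph describes "A pilot randomized placebo-controlled cross-over study" and sets out the comparison as follows: "Eligible subjects with spinal cord injury were studied on three separate occasions: (1) Buspirone vs. Trazodone vs. placebo for 2 weeks". The endpoint is the CO₂ reserve, "which is a marker to measure susceptibility to hypocapnic central apnea".

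The Statistical Data analysis paragraph then gives two inferential statements. The first is "The primary analysis was repeated measure analysis of variance". The second is the fallback: "In the absence of normal distribution of data, appropriate non-parametric tests were used". Neither gives the levels of the treatment factor, a contrast, a multiplicity rule or a period term.

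The Study Protocol paragraph closes with "For the baseline hypocapnic apneic threshold the nasal mechanical ventilation study obtained from specific aim 1 was used as a baseline". That labels the aim 1 study as the baseline but gives it no place in the analysis model.

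**The concern.** A placebo period is included so that each drug can be compared with placebo. An overall F test on three levels does not make that comparison. If it rejects, at least one drug differs from placebo, but the test does not say which one, in which direction or by how much. If it does not reject, there is no estimate or interval for either drug. The fallback leaves the same gap, because the tests are unnamed and so are the pairs to which they would apply.

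What is at stake is the trial's main conclusion. Without a stated contrast, the choice of pairs, adjustment and reference condition can be made after the results are seen.

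Two lesser gaps sit beside this one. Each participant is studied on three successive occasions, and no period term is named. The aim 1 study lies outside the randomised periods, and its place in the analysis is open.

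**Working it through.** **Inputs.** From the documents: three treatments, three occasions, one primary endpoint, repeated-measures ANOVA. They give no sample size, SD, alpha, drift or sequence allocation, and no power figure to reproduce. Everything below therefore rests on assumptions: n = 10, 15 or 20; two-sided 5%; normal data with independent within-subject errors of SD 1; no carryover. Triplets are in the order n = 10/15/20.

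**1. The F test cannot tell the cases apart.** The noncentrality is n × Σ(τ − mean τ)². With (placebo, buspirone, trazodone) effects of (0, 1, 0), the mean is 1/3 and the sum is 1/9 + 4/9 + 1/9 = 0.667. Effects of (0, 0, 1) also give 0.667. Effects of (0, 1, 1) have mean 2/3 and sum 4/9 + 1/9 + 1/9 = 0.667. With a period term and balanced sequences the residual df is 3n − n − 2 − 2 = 2n − 4, which is 16/26/36. Power from the noncentral F distribution is 54.6/76.5/89.0% in all three cases. A significant result is equally likely whichever drug works.

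**2. What two named contrasts give.** On the same df the ordinary t critical values are 2.120/2.056/2.028. The Dunnett values for two contrasts sharing a placebo (correlation 0.5) are 2.424/2.338/2.302. The ratio, about 1.14, is the widening of the intervals.

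| | n = 10 | n = 15 | n = 20 |
|---|---|---|---|
| Power, one drug at 1 SD, unadjusted | 55% | 75% | 87% |
| Power, one drug at 1 SD, Dunnett | 44% | 65% | 80% |
| Family error, unadjusted | 8.9% | 8.9% | 9.1% |
| Family error, Dunnett | 5.0% | 5.0% | 5.1% |

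The powers and family errors are simulated. If the two tests were independent, the unadjusted family error would be 1 − 0.95² = 9.75%. The shared placebo brings it down to about 9%.

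**3. Period term (secondary).** Suppose a linear drift of d SD per period and balanced sequences. Without a period term, the period sum of squares, 2nd², falls into an error with 2n − 2 df. At d = 0.5 and n = 10 that is 5/18 = 0.28, so the error variance rises from 1 to about 1.28. At d = 0.25 it is 1.25/18 = 0.07. Simulated Dunnett power for one drug at 1 SD:

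| Drift per period, balanced blocks of 6 | Without term | With term |
|---|---|---|
| 0.25 SD | 42/63/78% | 44/65/80% |
| 0.5 SD | 35/55/71% | 44/65/80% |

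With no drug effect and 0.5 SD drift, the F test without the term rejects in 2.7/2.8/2.6% of balanced trials, so it is conservative there. Under simple randomisation it rejects in about 4–5%, averaged over allocations, so it is no longer clearly conservative. The documents do not say how sequences were allocated.

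**4. Aim 1 baseline (secondary and conditional).** Suppose this study were entered as a fourth level and there were no difference among the three treatments. At n = 12, a shift of 0.5 to 1.0 SD between baseline and the treatment periods would make the overall F test significant in 19% to 65% of trials. The three-level test stays near 5%. Nothing in the documents shows that the baseline was used in this way.

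**The case against.** The best defence is that silence is not a wrong choice. The analysis paragraph does not say that the work stopped at the F test. A placebo-controlled design comparing "Buspirone vs. Trazodone vs. placebo for 2 weeks" suggests the comparator, and follow-up comparisons after an ANOVA are common. This stands in part: a reader might infer that drug-versus-placebo comparisons were never made, and the documents do not support that. What they support is that none was specified. Which pairs, which adjustment and which reference condition all stay open, and the fallback settles none of them.

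Second, this is a pilot, and multiplicity adjustment in a pilot is a matter of preference. That is accepted: Dunnett is one option, and clearly labelled unadjusted intervals are another. Being a pilot does not remove the need to say what the primary comparison is.

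Third, the period point is modest. At 0.25 SD drift the term gains about 2 points, and under simple randomisation with no drift it costs 5/4/2 points. That is also accepted, and it is why the point is secondary. A reader might infer that leaving out the term makes the test produce false positives. The simulations do not show that: the rate is at or below about 5%. The documents do not allow a flat reassurance either, because a particular unbalanced allocation combined with drift could bias a contrast.

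Finally, a reader might infer that the baseline was a level of the ANOVA. The three occasions and three named treatments favour a three-level reading.

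**Conclusion.** The point holds as a gap in the stated primary analysis. The named method, taken as written, does not answer whether buspirone or trazodone differs from placebo, and neither the primary method nor the fallback names a contrast that would. This conclusion rests on the text alone and needs no assumed figures.

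The sizes do rest on assumptions about sample size, effect and drift that the documents neither give nor contradict. They show that F power is the same whichever drug works, and that a period term is worth about 9/10/9 points of Dunnett power at 0.5 SD drift with balanced sequences (44 − 35, 65 − 55, 80 − 71) but only about 2 points at 0.25 SD. They are not estimates for this trial. The period term and the baseline role deserve a sentence each, and neither is evidence that the reported result is wrong.

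**What to change.** **Primary model.** Analyse the three randomised periods with a three-level treatment factor (placebo, buspirone, trazodone) and terms for participant and period. Name buspirone minus placebo and trazodone minus placebo as the two primary contrasts, each with a 95% interval.

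**Multiplicity.** Choose one approach and use it for both tests and intervals: Dunnett-adjusted, or unadjusted and labelled so, with a family error of about 9%.

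**Fallback.** Use the same two paired contrasts. If adjusting, one option is signed-rank tests at 2.5% each with 97.5% Hodges-Lehmann intervals. State that these do not adjust for period.

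**Baseline.** State the role of the aim 1 study. Keep it descriptive or secondary, and out of the primary treatment factor.

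**Labelling.** The text is in the past tense, so present the change as a clarification (if this is what was done) or as a re-analysis (if not), and report the original ANOVA beside it.

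**Cost.** No new data are needed. If Dunnett is used, intervals are about 14% wider and power for one drug at 1 SD falls from 55/75/87% to 44/65/80%. With no drift, the period term costs 0.3 to 1.5 points of Dunnett power in balanced blocks, and up to about 5 points under simple randomisation at n = 10. The signed-rank fallback at 2.5% is weaker on normal data: 32/55/74% with no drift and 24/44/63% at 0.5 SD drift. No primary claim of change from baseline could be made.

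**Limit.** The period term does not remove carryover. The Study Protocol paragraph mentions washout only at the second occasion ("to determine the hypocapnic apneic threshold followed by two weeks washout"), and all the powers above assume no carryover.
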